18. Current continued use, or anticipated continued medical indication for hepatotoxic agents, including but not limited to amiodarone, methotrexate, and anticonvulsants and antimicrobials with elevated hepatotoxic potential.
NOTE: Low doses or limited duration of these agents (i.e., ≤ 14 days) is not exclusionary.
19. Active drug or alcohol use or dependence that, in the opinion of the investigator, would interfere with adherence to study requirements.
20. Serious illness requiring systemic treatment and/or hospitalization within 30 days prior to study entry that in the judgement of the investigator may compromise study participation or pose additional risks to the participant.
21. Any other condition that, in the opinion of the clinical investigator or sponsor, might compromise any aspect of this trial.

C.5. STUDY TREATMENT PLAN

C.5.1. Study Medication (rIL-2)

Proleukin® (Prometheus Laboratories) is provided as a sterile, white to off-white, lyophilized cake in glass vials, each containing 22 MIU.

C.5.1.1. Dosage and Cycle Guidelines

Participants will receive rIL-2 at an initial dose of approximately 5 MIU twice daily for 4 consecutive days every 8 weeks (8 cycles total). Each vial will be reconstituted according to the package insert instructions using 1.2 mL of diluent, and 4 doses will be obtained from each vial. Occasionally, the reconstituted volume that can be drawn from the vial may result in doses that are slightly smaller than 5 MIU each. These small deviations from the total intended dose are biologically inconsequential and do not constitute protocol deviations.

C.5.1.2. Preparation of rIL-2 for Subcutaneous Administration

The Investigational Pharmacy will reconstitute rIL-2 at the beginning of each cycle for each participant, and draw each individual dose into tuberculin syringes under sterile conditions. As was done in two previous large trials of rIL-2 in HIV-infected participants(19), all eight doses will be prepared, labeled, and delivered to the participant on day 0 of each cycle. This procedure may be modified in the course of

the study if deemed necessary by the Investigational Pharmacy, the investigators, or a regulatory authority, including the option to prepare a smaller number of doses in advance. In that case, pre-filled syringes may be shipped by fast courier to the participant's residence.

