Participants will be taught to give themselves rIL-2 injections. This will require substantial clinician support in terms of both time spent instructing participants and in availability to answer participant questions and respond to participant concerns about injections and side effects. Refer to the Manual of Operating Procedures (MOPS) document for further details on initial and subsequent dose administration

C.5.2. Guidelines for Dosage Modification

Participants will be monitored closely for side effects of rIL-2. Participants who experience dose-limiting side effects may have their rIL-2 temporarily interrupted or their dose reduced.

The Manual of Operations (MOPs) includes a list of toxicities for which the investigator may choose to temporarily interrupt or dose-reduce rIL-2 (hereinafter, dose-limiting toxicities). An outline of criteria for certain specific potential adverse events are provided in section E.1. Briefly, the following guidelines apply:

- For toxicities during the 4-consecutive-day administration of rIL-2 that are considered dose-limiting, the remaining rIL-2 doses of that cycle of therapy will be interrupted until the dose-limiting toxicity is no longer considered dose-limiting.
- In some circumstances, a toxicity may be regarded as dose-limiting in the opinion of the investigator, even if it does not meet the above-mentioned criteria. In these instances, the clinical judgment of the investigator takes precedence.
- When rIL-2 treatment is reinitiated after interruption because of a dose-limiting toxicity, the dose will be reduced by up to 1.5 MIU per injection (3 MIU/day). If the reduced dose results in a dose-limiting toxicity during the same cycle, rIL-2 therapy will again be interrupted. Further dose reduction, if necessary, will be made in the same fashion.
- If a participant cannot tolerate an rIL-2 dose of 2 MIU twice a day then rIL-2 therapy will be permanently stopped.
- If, after a dose reduction, a participant completes a treatment cycle without significant toxicity, then escalation of the rIL-2 dose at the next cycle may occur by an increment of up to 1.5 MIU/dose (3 MIU/day).
- The total duration of a course of rIL-2 will not be extended for doses missed as a result of toxicity or any other reason.

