E.1. MANAGEMENT OF SPECIFIC ADVERSE EVENTS

The Guidelines for Dose Modification, (protocol section C.5.2), apply to all of the scenarios listed in this section.

E.1.1. Serious Infections

All subjects will be monitored for signs or symptoms of a serious or local infection at each visit. All subjects who develop a serious infection while on study will be referred for immediate medical care to a qualified healthcare professional. Participants who develop any of the following infectious events will be required to discontinue study treatment:

- Tuberculosis, pulmonary or extrapulmonary
- Non-tuberculous mycobacterial infection, disseminated or extrapulmonary
- *Pneumocystis jirovecii* pneumonia
- Coccidioidomycosis, disseminated or extrapulmonary
- Cryptococcosis, extrapulmonary
- Cryptosporidiosis or isosporiasis, chronic intestinal (greater than 1 month's duration)
- Cytomegalovirus disease (other than liver, spleen, or lymph nodes) and including retinitis with loss of vision
- Histoplasmosis, disseminated or extrapulmonary
- Kaposi's sarcoma
- Lymphoma, Burkitt's or immunoblastic, regardless of anatomical location
- Lymphoma, primary of brain
- Progressive multifocal leukoencephalopathy
- Toxoplasmosis of brain
- Herpes zoster reactivation involving more than one dermatome or visceral involvement including but not limited to viral pneumonia, encephalitis and hepatitis.
- Any serious infection that is considered life-threatening or requires inpatient treatment. Participants who experience other serious infections not listed above that do not require inpatient treatment and are not considered life-threatening will have study treatment temporarily stopped until the infection is controlled. These subjects may restart study drug once the infection is controlled.

Other infections, including local infections, will also require referral to qualified medical treatment. The study principal investigator, in consultation with the SMC if necessary, will determine if an infection not listed above warrants permanent treatment discontinuation.

E.1.2. Acute Hypersensitivity Reactions

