To minimize the risk of a severe, immediate-type hypersensitivity reaction or capillary leak syndrome, the first dose of study agent will be administered in the Special Immunology Unit by personnel with experience administering rIL-2 to over 50 participants in the SILCAAT and ACTG 328 trials. Participants will be monitored for a minimum of 30 minutes following the first dose of study drug by personnel with life support training and access to adequate life support equipment and resuscitation medication.

Development of a grade ≥ 3 hypersensitivity reaction, a grade 2 hypersensitivity reaction that includes manifestations of angioedema, or suspected or confirmed capillary leak syndrome will require permanent treatment discontinuation.

E.1.3. Neutropenia

Participants who develop neutropenia will be referred for treatment by a qualified healthcare professional. Volunteers with an ANC $< 2,000$ cells/mm 3 at screening will be excluded.

- Should the ANC decrease to ≥ 500 but $\leq 1,000$ cells/mm 3 , the rIL-2 dose will be interrupted until the ANC is $> 1,000$ cells/mm 3 and then rIL-2 will be restarted at 3.5 million units twice daily. If the ANC then remains above 1,000 cells/mm 3 , this dose will be continued until the end of study.
- If the ANC drops to ≥ 500 but $\leq 1,000$ cells/mm 3 while on the reduced dose of 3.5 million units twice daily, rIL2 will be discontinued until the ANC reaches 1,000 cells/mm 3 , and then resumed at a dose of 2 million units twice daily. If the ANC then remains above 1,000 cells/mm 3 , this dose will be continued until the end of study. If the ANC falls again to $\leq 1,000$ cells/mm 3 while on the reduced 2 million unit twice daily dose, rIL2 will be permanently discontinued.
- Should the ANC decrease to < 500 cells/mm 3 , rIL-2 will be permanently discontinued.

E.1.4. Thrombocytopenia

Participants who develop thrombocytopenia will be referred for treatment by a qualified healthcare professional. Volunteers with platelet counts $< 150,000$ /mm 3 will be excluded.

- Should the platelet count decrease to $\geq 50,000$ but $\leq 100,000$ /mm 3 the rIL-2 dose will be interrupted until the platelet count is $> 100,000$ /mm 3 and then rIL-2 will be restarted at 3.5 million units twice daily. If the platelet count then remains above 100,000 /mm 3 , this dose will be continued until the end of study.

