- If a participant develops anti-Tpo antibody levels that are above the normal reference range of the laboratory, rIL-2 will be permanently discontinued.
- If a participant develops clinical signs or symptoms of hypo- or hyperthyroidism, rIL-2 will be permanently discontinued.

E.1.7. Renal Dysfunction

Participants who develop evidence of renal dysfunction will be referred for treatment by a qualified healthcare professional. Volunteers with serum creatinine $> 1.5 \text{ mg/dL}$ at screening will be excluded.

- Should serum creatinine increase to $> 2.0 \text{ mg/dL}$ but $\leq 3 \text{ mg/dL}$, rIL-2 will be interrupted. rIL-2 may be resumed at 3.5 million units twice daily when creatinine falls to $< 1.5 \text{ mg/dL}$. If creatinine remains $\leq 1.5 \text{ mg/dL}$ on the reduced dose of 3.5 million units twice daily, this dose will be continued to the end of study.
- If serum creatinine rises again to $> 1.5 \text{ mg/dL}$ while on the reduced dose of 3.5 million units twice daily, rIL-2 will be interrupted until it falls to $< 1.5 \text{ mg/dL}$ and then resumed at a dose of 2 million units twice daily. If serum creatinine then remains below 1.5 mg/dL , this dose

- will be continued to the end of study. If serum creatinine rises again to >1.5 mg/dL while on the reduced 2 million unit twice daily dose, rIL2 will be permanently discontinued.
- Should serum creatinine rise to >3 mg/dL, rIL-2 will be discontinued permanently

E.1.8. Malignant Conditions

All participants will be monitored for signs or symptoms of a malignant condition at each visit, and referred for treatment by a qualified healthcare provider if evidence of malignancy is found. Volunteers with a history of malignant disease that has not been fully resected and considered cured or in remission for at least 5 years will be excluded. Participants who develop a malignancy other than a basal cell skin carcinoma requiring no more than local excision during study will be required to discontinue study treatment permanently.

E.1.9. Viral Reactivation

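### The first-episode restart dose in E.1.3 and E.1.4 ignores the dose in use, and conflicts with C.5.2 for a participant already at 2 MIU because of a different toxicity

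*Combined protocol and SAP*

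**What the plan says.** Treatment starts at about 5 MIU twice daily (C.5.1.1). Sections E.1.3 (ANC), E.1.4 (platelets), E.1.5 (AST/ALT) and E.1.7 (creatinine) each set out a ladder of dose steps, and I.6.1.4 repeats them.

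- **First step, ANC and platelets.** Treatment is interrupted until the count recovers, "and then rIL-2 will be restarted at 3.5 million units twice daily". The wording is mandatory and carries no condition on the current dose.
- **First step, AST/ALT and creatinine.** The same dose is named, but restart is optional. For creatinine, "rIL-2 may be resumed at 3.5 million units twice daily when creatinine falls to" below 1.5 mg/dL.
- **Later steps.** The second step applies to a participant on 3.5 MIU and leads to 2 MIU. The third applies on 2 MIU and is a permanent stop, worded for a value that falls or rises *again*. Each ladder keeps its reduced dose to the end of study if its own laboratory value stays acceptable.

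C.5.2 sets the general rule relative to the current dose: "When rIL-2 treatment is reinitiated after interruption because of a dose-limiting toxicity, the dose will be reduced by up to 1.5 MIU per injection". It adds: "If a participant cannot tolerate an rIL-2 dose of 2 MIU twice a day then rIL-2 therapy will be permanently stopped". It allows an increase after a dose reduction only when the participant "completes a treatment cycle without significant toxicity, then escalation of the rIL-2 dose at the next cycle may occur". E.1 opens by tying the two together: "The Guidelines for Dose Modification, (protocol section C.5.2), apply to all of the scenarios listed in this section". It gives no order of precedence.

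**The concern.** Each ladder reads as if it were the only one in use and the participant entered it on 5 MIU. The text does not say what happens when a second, different laboratory toxicity occurs in someone already reduced. Read literally, the first step then returns a participant at 2 MIU to 3.5 MIU straight after a new toxicity. For AST/ALT and creatinine it permits the same rise, or leaves a participant at 3.5 MIU unchanged.

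The main stake is safety: two clinicians following the text could give different doses for the same results. There is a smaller statistical cost. The secondary model in C.2.1(b) accounts for total dose through the number of cycles received, so differences in dose per injection that arise from ambiguous wording do not enter it.

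**Working it through.** **Reproducing the ladder doses.** From the starting dose with the full C.5.2 decrement: 5 − 1.5 = 3.5 MIU, then 3.5 − 1.5 = 2 MIU. These are the doses in the ladders, so E.1 and C.5.2 agree for a participant who enters a ladder on 5 MIU.

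**Applying the rules to a first event on a new ladder, by dose in use** (MIU per injection, twice daily):

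| Dose in use | First step of the new ladder | C.5.2 | Ladder that set the current dose |
|---|---|---|---|
| 5 | 3.5 | reduction, to 3.5 at the full step | none |
| 3.5 | AST/ALT, creatinine: 3.5 (optional), no reduction. ANC, platelets: 3.5, but the second step can also be read to apply and gives 2 | reduction, to 2 at the full step | 3.5 to end of study |
| 2 | 3.5 (mandatory for ANC and platelets, optional for AST/ALT and creatinine) | permanent stop if 2 is not tolerated; a further full step would be 2 − 1.5 = 0.5, below that floor; no rise on restart | 2 to end of study |

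- **At 5 MIU** there is no conflict.
- **At 3.5 MIU** the conflict is clear for AST/ALT and creatinine, whose second step is worded for a repeat event. It is weak for ANC and platelets, whose second step does not say *again* and so can take in a first event.
- **At 2 MIU** the three columns cannot all be followed. The third step does not remove the conflict, because it is worded for a repeat of the same abnormality.

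**Example.** A participant is at 2 MIU after two platelet episodes and then has a first ANC of 800. E.1.3 gives 3.5 MIU, C.5.2 gives a reduction or a stop, and E.1.4 gives 2 MIU to the end of study.

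**Size of the rise at 2 MIU.** 3.5 − 2 = 1.5 MIU per injection; 3.5 / 2 = 1.75, or +75%. Per day: 2 × 2 = 4 to 2 × 3.5 = 7 MIU. Per eight-dose cycle: 8 × 2 = 16 to 8 × 3.5 = 28 MIU.

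**How many participants.** The documents give no rates for these laboratory events. Suppose, purely as an assumption, that each of the four ladders is triggered independently with probability p. The chance of meeting at least two is 1 − (1 − p)^4 − 4p(1 − p)^3. For p = 0.05, 0.10 and 0.20 this is 0.014, 0.052 and 0.181, or about 0.3, 1.0 and 3.6 of 20 participants. This does not estimate how often the rise would occur. Between two laboratory ladders the rise needs at least three episodes in order (two on one ladder, then a first on another) with no permanent stop between them, so only some of these participants could reach it. The count also leaves out participants reduced under C.5.2 for non-laboratory toxicity.

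**The case against.** The strongest reply is that the protocol already supplies the answer. C.5.2 is applied to every E.1 scenario, it describes E.1 as an outline, and its stop for intolerance of 2 MIU is not limited to one cause. The ladder doses are C.5.2 applied from 5 MIU, so the first step plainly has that participant in mind. An investigator who follows C.5.2 avoids the rise. The investigators also review all grade 2 or higher events in real time (section G). Scheduled on-treatment safety panels are few: day 0 of eight cycles and day 7 of cycles 1, 4 and 8, so 8 + 3 = 11. Dose changes are foreseen, and the doses actually given are recorded (D.3.4.8). The Manual of Operations, cited for dose modification, may deal with overlapping toxicities.

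Much of this stands and limits the weight of the point. It does not remove the conflict. If the first step silently assumes 5 MIU, E.1 has no step for a first, different event at 2 MIU, and that gap needs the same edit. If C.5.2 governs, the mandatory restart wording in E.1.3 and E.1.4 is wrong for these participants. The escalation clause in C.5.2 does not help, because it requires a cycle without significant toxicity. The precedence that C.5.2 gives to clinical judgment concerns whether a toxicity counts as dose-limiting, not the restart dose.

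A reader might infer more than the documents support:

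- **That the plan intends to raise the dose after a toxicity.** Nothing indicates this; the steps read as written for one toxicity at a time.
- **That all four ladders force the restart.** Only ANC and platelets do.
- **That different sites would diverge.** The supplied text describes recruitment, clinical laboratories, leukapheresis and ethics review centred on one institution, so divergence between clinicians is the realistic form.

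**Conclusion.** The conflict is real but narrow. It is firmest for a first ANC or platelet event in a participant already at 2 MIU because of another toxicity: one mandatory instruction raises the dose by 75% per injection, while C.5.2 and the other ladder point elsewhere. AST/ALT and creatinine carry the same conflict in optional form, at 2 MIU (a rise) and at 3.5 MIU (no reduction). For ANC and platelets at 3.5 MIU it is weak.

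The conclusion rests on the literal wording of the first steps, on E.1 giving no order of precedence, and on the supplied text alone, without the Manual of Operations. The number of participants affected cannot be derived from the documents and is probably small. A reader might rank this as something that must be resolved before the trial can proceed. The route through C.5.2, the sequence of events required and the unseen manual do not support that. It is a moderate safety-wording reconciliation.

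**What to change.** Reconcile the first-episode steps in E.1.3, E.1.4, E.1.5, E.1.7 and I.6.1.4 with C.5.2. Each step should state how it applies to a participant already below 5 MIU because of a different toxicity, and the protocol should name one section as governing when the instructions differ. Check the Manual of Operations against the result. Which dose or stopping rule should apply is for the sponsor and investigators; none is proposed here. The cost is wording in a protocol amendment, with no added visits, tests or participants.

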3. HIV-1 infection, documented by and FDA-approved ELISA, EIA, or rapid antibody detection method, and confirmed by a second approved antibody-based test or by a positive approved HIV RNA detection assay.
4. CD4+ T cell count ≥ 350 cells/mm 3 .
5. HIV-1 RNA < 50 copies/mL obtained within 60 days prior to study entry performed with an FDA-approved HIV-1 RNA assay.
6. Adequate venous access and no other contraindications for leukapheresis.
7. Absolute neutrophil count (ANC) ≥ 1500 /mm 3 .
8. Hemoglobin level >10 g/dL.
9. Platelet count $\geq 100,000$ /mm 3 .

² Accelevir, data on file

10. Serum creatinine ≤ 1.5 mg/dL
11. AST and ALT < 2.5 times the upper limit of normal
12. TSH, T3, and T4 levels within the normal range of the processing laboratory.
13. Anti-thyrosine peroxidase (TPO) antibodies within the normal range of the processing laboratory.
14. Willing to comply with study-mandated evaluations; including not changing antiretroviral regimen (unless medically indicated) during the study period.
15. All participants must have received HAART, and had viral loads below the limit of quantification of the assay for at least 1 year. Participants who had intermittent isolated episodes of detectable low-level viremia < 500 copies RNA/mL flanked by viral loads below the limit of quantification of the assay will remain eligible.
16. On a stable combination antiretroviral regimen (no changes to treatment within 4 weeks of enrollment) including at least 3 medications and willing to continue on current antiretroviral therapy for the duration of the study, unless otherwise medically indicated.

C.4. EXCLUSION CRITERIA

1. Childbearing potential for female participants. For the purposes of this study, a woman is considered to be of childbearing potential if she is not postmenarchial, has not had a documented surgical sterilization procedure, has an intact uterus and at least 1 ovary, and has had a spontaneous menstrual period in the last 2 years.
2. Acute or chronic hepatitis C infection, defined as a positive plasma HCV RNA using any FDA-approved qualitative or quantitative test in a participant with a positive HCV antibody (HCV RNA testing is not required in participants with a negative HCV antibody). Participants who have completed a course of a direct-acting antiviral agent for hepatitis C and have a confirmed plasma HCV RNA level below the limit of detection of the assay 12 weeks or longer after completion of therapy will be eligible.

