- If the platelet count drops to $\geq 50,000$ but $\leq 100,000$ /mm 3 while on the reduced dose of 3.5 million units twice daily, rIL2 will be discontinued until the platelet count reaches 100,000/mm 3 and then resumed at a dose of 2 million units twice daily. If the platelet count then remains above 100,000 /mm 3 , this dose will be continued until the end of study. If the platelet count falls again to $\leq 100,000$ /mm 3 while on the reduced 2 million unit twice daily dose, rIL2 will be permanently discontinued.
- Should the platelet count decrease to $< 50,000$ /mm 3 , rIL-2 will be permanently discontinued.

E.1.5. AST and ALT Abnormalities

Participants who develop AST or ALT elevations will be referred for treatment by a qualified healthcare professional. Volunteers with AST or ALT levels $> 2.5 \times$ ULN at screening will be excluded.

- Volunteers with cirrhosis, severe liver disease, or active hepatitis B or C infection will be excluded from the study.
- Should AST or ALT values rise to $> 3 \times$ ULN, rIL-2 will be interrupted. rIL-2 may be resumed at 3.5 million units twice daily when AST or ALT fall to $< 2 \times$ ULN. If AST and ALT values then remain below $3 \times$ ULN, this dose will be continued to the end of study.
- If AST or ALT values rise again to $> 3 \times$ ULN while on the reduced dose of 3.5 million units twice daily, rIL-2 will be interrupted until AST and ALT fall to $< 2 \times$ ULN and then resumed at a dose of 2 million units twice daily. If AST and ALT values then remain below $3 \times$ ULN, this dose will be continued to the end of study. If AST or ALT levels rise again to $> 3 \times$ ULN while on the reduced 2 million unit twice daily dose, rIL2 will be permanently discontinued.
- If ALT values rise again to $> 3 \times$ ULN while the patient is receiving 2 million units twice daily, rIL-2 will be discontinued permanently.
- Should AST or ALT values rise to $> 5 \times$ ULN, rIL2 will be permanently discontinued.

E.1.6. Thyroid Test Abnormalities

Participants who develop thyroid function test (TFT) abnormalities will be referred for treatment by a qualified healthcare professional. Volunteers with abnormal TFTs or levels of anti-thyroid antibodies (anti-Tpo) at screening will be excluded.

- If a participant develops a TSH level $> 3.98 \text{ mIU/L}$, rIL-2 will be permanently discontinued.
- If T3 or T4 levels are outside the normal reference range of the laboratory, rIL-2 will be permanently discontinued.

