I.6.1.3. Risk Mitigation Strategy for Thromboembolic Disease

In the ESPRIT trial but not among participants in the SILCAAT trial, there was an increased occurrence of vascular events (but not in cardiac disorders) that were seen among 40 of 466 patients receiving IL-2 plus ART and 14 of 386 receiving ART alone. The most frequent vascular event was deep vein thrombosis seen in 10 IL-2 plus ART recipients and in 2 ART alone recipients. To mitigate risk for vascular events in this trial, persons with a history of venous thrombosis will be excluded from participation and at each visit, signs and symptoms of venous thrombosis will be sought.

I.6.1.4. Risk Mitigation Strategy for Laboratory Abnormalities

I.6.1.4.1. Neutropenia

The risk mitigation plan for neutropenia includes:

- Participants with an ANC <1500 cells/mm³ will not be permitted to enroll in the study;
- ANC will be measured at each clinic visit
- Should the ANC decrease to ≥500 but ≤1,000 cells/mm³, the rIL-2 dose will be interrupted until the ANC is >1,000 cells/mm³ and then rIL-2 will be restarted at 3.5 million units twice daily. If the ANC remains above 1,000 cells/mm³, this dose will be continued until the end of the study.
- Should the ANC decrease ≥500 but ≤1,000 cells/mm³ while on the reduced dose of 3.5 million units twice daily, rIL2 will be discontinued until the ANC reaches 1,000 cells/mm³, and then resumed at a dose of 2 million units twice daily. If the ANC then remains above 1,000 cells/mm³, this dose will be continued until the end of study. If the ANC falls again to ≤1,000 cells/mm³ while on the reduced 2 million unit twice daily dose, rIL2 will be permanently discontinued.
- Should the ANC decrease to <500 cells/mm³, rIL_2 will be discontinued.

I.6.1.4.2. Thrombocytopenia

The risk mitigation plan for thrombocytopenia includes:

- Participants with a platelet count <150,000/mm³ will not be enrolled in the study;
- Platelet counts will be measured at each clinic visit;
- Should the platelet count decrease to ≥50,000 but ≤100,000/mm³ the rIL-2 dose will be interrupted until the platelet count is >100,000/mm³ and then IL-2 will be restarted at 3.5 million units twice daily. If the platelet count remains above 100,000 /mm³, this dose will continue until the end of the study.

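### Three eligibility rules conflict between sections: the platelet floor (100,000 or 150,000/mm³), the ANC cut-off in E.1.3, and the C.4 definition of childbearing potential

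*Combined protocol and SAP*

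**What the plan says.** **Platelets.** Item 9 of the inclusion criteria, in both the Synopsis and C.3, reads "Platelet count $\geq 100,000$ /mm 3". E.1.4 (Thrombocytopenia) says "Volunteers with platelet counts $< 150,000$ /mm 3 will be excluded", and I.6.1.4.2 says "Participants with a platelet count <150,000/mm³ will not be enrolled in the study". Both safety sections also set the first dosing action. I.6.1.4.2 puts it as "Should the platelet count decrease to ≥50,000 but ≤100,000/mm³ the rIL-2 dose will be interrupted", and E.1.4 gives the same band, adding that "the rIL-2 dose will be interrupted until the platelet count is $> 100,000$ /mm 3". A count below 50,000/mm³ ends treatment.

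**Neutrophils (ANC).** Item 7 of the Synopsis and C.3 inclusion lists admits counts of 1,500/mm³ or more. I.6.1.1 and I.6.1.4.1 exclude counts below 1,500. E.1.3 excludes volunteers below 2,000 at screening.

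**Childbearing potential.** Women of childbearing potential are excluded. The Synopsis (exclusion item 1) defines the term by four joint conditions: being postmenarchial, no documented surgical sterilization, an intact uterus with at least one ovary, and a spontaneous period in the last 2 years. C.4 item 1 gives the same four but puts *not* before postmenarchial. E.3 restates that women of reproductive potential are excluded.

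**The concern.** These rules decide who may be given rIL-2. Staff who screen from the Synopsis or C.3 would enrol a volunteer with 120,000 platelets/mm³ and would have no reason to look for a stricter floor in an adverse-event section. Someone working from E.1.4 or I.6.1.4.2 would turn the same person away. H.2 says the study follows the FDA-approved protocol, and on this question the protocol gives two answers. I.7.2 relies on the risk-mitigation strategy as protection for participants. I.6.1.4.2 is part of that strategy, so enrolment under C.3 in the disputed band would break a stated safeguard.

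The ANC discrepancy creates the same kind of conflict over a narrower range. The childbearing wording sits in the C.4 exclusion list, where a literal reading disables the exclusion.

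**Working it through.** No sample size, power or error rate enters here. The check is a comparison of the statements.

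**1. Platelets (per mm³)**

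| Section | Rule | Volunteer at 120,000 |
|---|---|---|
| Synopsis, inclusion item 9 | admit at 100,000 or more | eligible |
| C.3 item 9 | admit at 100,000 or more | eligible |
| E.1.4 | exclude below 150,000 | excluded |
| I.6.1.4.2 | exclude below 150,000 | excluded |

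The conflict band is the overlap of counts at or above 100,000 with counts below 150,000, that is 100,000 to 149,999. It is two statements against two, so neither value stands out as a slip. The lowest floor that satisfies all four is max(100,000, 150,000) = 150,000.

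Gap between the entry floor and the first interruption threshold of 100,000:
- floor 100,000: 100,000 − 100,000 = 0, so any fall from the lowest admissible count triggers interruption;
- floor 150,000: 150,000 − 100,000 = 50,000.

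Under E.1.4 a first interruption is followed by restart at 3.5 million units twice daily, a second by 2 million units, and a third fall to 100,000 or below by permanent discontinuation.

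**2. ANC (cells/mm³)**

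| Section | Rule |
|---|---|
| Synopsis, inclusion item 7 | admit at 1,500 or more |
| C.3 item 7 | admit at 1,500 or more |
| I.6.1.1 | exclude below 1,500 |
| I.6.1.4.1 | exclude below 1,500 |
| E.1.3 | exclude below 2,000 |

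The conflict band is 1,500 to 1,999. Only the two inclusion lists contradict E.1.3 directly. The two I.6 statements bar counts below 1,500 and do not in themselves declare 1,500 to 1,999 eligible. They do show which cut-off was in use: I.6.1.4.1 repeats the dose rules of E.1.3 almost step for step and pairs them with 1,500. E.1.3 is the outlier.

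**3. Childbearing potential**

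The C.4 conditions are joined, so all must hold. A spontaneous period in the last 2 years implies that a woman is postmenarchial. Requiring her also to be not postmenarchial leaves an empty set, so on a literal reading no woman is of childbearing potential. The Synopsis version, without *not*, is coherent and agrees with E.3.

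**The case against.** The strongest reply is that the platelet rules can be applied together: a volunteer must meet the inclusion list and not be barred elsewhere, which gives 150,000 and protects participants. That is a workable reading, but nothing instructs staff to adopt it. I.4 refers readers to the clinical protocol for the criteria, and the headed lists there are C.3 and C.4. That does not settle the matter, because E.1.4 belongs to the same protocol.

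It is also fair to say that the practical consequence is small. Blood counts are repeated at screening, at leukapheresis and on day 0 of every cycle. Interruption and stopping rules apply whichever floor is used, and C.4 item 21 allows exclusion for any other condition of concern. D.2.1 includes a pregnancy test at screening, although that detects a current pregnancy and does not replace the childbearing exclusion. These points limit the harm; they do not remove the contradictions.

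A reader might go further and infer that the zero gap at 100,000 proves that floor to be an error, because other tests leave room. For ANC, entry at 1,500 compares with "Should the ANC decrease to ≥500 but ≤1,000 cells/mm³, the rIL-2 dose will be interrupted". For transaminases, "AST and ALT < 2.5 times the upper limit of normal" compares with "Should AST or ALT values rise to $> 3 \times$ ULN, rIL-2 will be interrupted". The documents do not support that inference. C.3 requires normal T3, T4 and anti-TPO at entry, and E.1.6 stops treatment permanently when T3 or T4 leaves the normal range or anti-TPO rises above it. Under E.1.7, creatinine above 1.5 mg/dL interrupts treatment on the reduced dose, and 1.5 is also the entry limit. Zero gaps therefore occur elsewhere, and no section sets a target gap. The gap is a reason to prefer 150,000 as a default; it is not evidence of what was intended.

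A last objection is that the strictest value is preferred for platelets but not for ANC, where it would be 2,000. The evidence differs. Platelets are two statements against two, with both safety sections agreeing. For ANC one section stands alone, and its own counterpart in I.6 uses 1,500.

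**Conclusion.** The three conflicts are in the current text and are wrong as written. The platelet floor is the substantive one: counts of 100,000 to 149,999/mm³ are both admitted and excluded, and the documents do not show which was meant. The ANC figure in E.1.3 and the *not* in C.4 item 1 are errata whose intent can be recovered from the other sections.

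The matter should be corrected but does not threaten the trial's validity. A reader might infer that the analysis is compromised, or that ineligible people will have been treated. Neither follows: nothing here bears on the QVOA endpoint or the power statement, and the documents do not say how many volunteers fall in either disputed band. The conclusion assumes that no section ranks one set of criteria above another, and none was found that does. The Manual of Operations, which was not available, might give screening instructions, but it would not correct the protocol text.

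**What to change.** 1. **Platelets.** Use one value in the Synopsis, C.3, E.1.4 and I.6.1.4.2. The safer default is 150,000/mm³, entered as item 9 of both inclusion lists: it satisfies all four statements and keeps entry above the interruption threshold. If the sponsor intended 100,000, correct E.1.4 and I.6.1.4.2 instead.
2. **ANC.** In E.1.3, change the screening exclusion from below 2,000 to below 1,500 cells/mm³.
3. **Childbearing potential.** In C.4 item 1, delete *not* before postmenarchial.

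The cost is amendment wording. A 150,000 floor would make the eligible pool somewhat smaller; the loss is expected to be small but cannot be quantified from the documents.
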